#### Randomization

After the first two groups (one each of MFY and HLG), randomization occurs one week before the first class. A designated study team member will use the randomization feature of REDCap to randomize participants. The procedure involves a review of eligibility followed by an assignment to one of the groups.

### 6.2.3: Follow-up Visits

Following the eight-week program, participants will have self-report assessments 22 weeks after the program (Visit 13) and 36 weeks after the program (Visit 16, final evaluation).

## Visit 1

[Section 6.2.2](#), *Enrollment and Baseline Assessments*, provides a description of Visit 1.

## Visit 2

Study staff will send the study questionnaires via a link to parents and adolescents one week before the start of classes. Parents and adolescents will complete the online measures. Once measures are completed, study staff will notify the participants of their group assignment and logistics of participation (time, place, etc.)

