**Patient-Reported Outcomes Measurement Information System Pediatric Short Form (PROMIS Pediatric Short Form)**: The PROMIS Pediatric Short Form is a short 12-item survey designed to screen for depression. The PROMIS Pediatric Short Form will be used as a safety measure once participants are in the 8-week course to assess any changes in depressive symptoms. See [7. Safety Assessments](#) for more details about the PROMIS Pediatric Short Form being used as a safety measure for the study. A T score of 70 on the PROMIS depression measure will generate a referral to the study psychologist.

**Demographics:** The study is limited to adolescents experiencing subsyndromal depression. The demographic survey, administered at baseline, will collect data about each teen’s age, gender, race/ethnicity, years of education, and parental educational attainment.

**Qualitative measures:** We will collect two types of formal qualitative data: 1) Evaluation (focus) groups following each 8-week set of classes at the end of the last class; 2) Transcriptions of audio-recorded classes. The focus groups will address the following topics related to the teens’ experience with the programs, including:

- 1) Most memorable aspects of program (e.g. most favorite and least favorite aspects);
- 2) Whether they would recommend it to a friend;
- 3) Usefulness, challenges and recommended changes including in-class and out-of-class assignments;
- 4) Usefulness of the program for management of stress, mood, and well-being in daily life;
- 5) Tools that might help them maintain practices; and
- 6) Unfulfilled expectations of the program.

Each focus group will be audio-recorded and transcribed.

Table 2. Study measures		
MEASURE	CONSTRUCT	TIMING
Inclusion/Exclusion Criteria		
QIDS-SR	Depression screening	Pre-screening
Diagnostic Interview Schedule for Children (DISC-IV)	Screening for serious psychopathology	Screening visit
Primary Outcomes		
PROMIS Pediatric Depression Short Form v1.1	Incident major depression	Weekly from the beginning of the intervention
Secondary Outcomes		
Short Mood and Feelings Questionnaire (SMFQ-C)	Depression scores change	Visit 2, Visit 6, Visit 10, Visit 13, Visit 16
Brief Resiliency Scale (BRS)	Resiliency	Visit 2, Visit 6, Visit 10, Visit 13, Visit 16
Exploratory Mediating Measures		
Adolescent Cognitive Style Questionnaire (ASCSQ)	Cognitive Style	Visit 2, Visit 6, Visit 10, Visit 13, Visit 16

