## 6. STUDY PROCEDURES

### 6.1: Schedule of Evaluations

Participants will follow the schedule in Table 3 to complete consenting and assessments:

Table 3. Schedule of Evaluations												
Assessment	Visit 1 Screen and Baseline	Before Visit 2 (online)	Visit 2 (W0)	Daily (W0-8)	Visits 3-5 (W1-3)	Visit 6 (W4)	Visits 7-9 (W5-7)	Visit 10 (W8)	Visit 11-12 (W13, 17)	Visit 13 (W22)	Visit 14-15 (W27, 32)	Visit 16 FINAL (W36)
Informed Consent	X											
Demographics	X											
Enrollment	X											
Psychological	X											
Inclusion/Exclusio	X											
Questionnaires		X				X		X		X		X
Randomization		X										
Credibility			X									
Daily practice diary				X								
Weekly practice									X	X	X	X
Weekly depression			X		X	X	X	X	X	X	X	X
Focus Group								X				X
Parent measures		X						X		X		X

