### 7.1: Specification of Safety Parameters

Combined SMFQ-C / SMFQ-P scores of 12 is the recommended cut-off value for MDD; this value or greater will generate follow-up with the study psychologist. In addition, a T score of 70 or an increase of 3 standard deviations from the baseline score on the PROMIS depression measure will generate a referral to the study psychologist.

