## 9.6: Data Analyses

### 9.6.1 Exploratory analyses of outcomes and mediators.

Exploratory analyses will involve first examining variable distributions and missing data patterns. Next, we will conduct exploratory analyses to assess patterns of change associated with participation in the programs. The study is not expected to produce a quantity of data large enough to have adequate power to detect significant effects of the MFY program compared to the TFY control program. However, trends in incident depression (primary outcome, PROMIS Pediatric Depression Scale), change in depression scores (combined SMFQ-C, PROMIS Pediatric Depression Score) resilience (secondary outcome), and potential mediators will be examined by program arm.

To assess incident depression, we will use exploratory nonparametric (Kaplan-Meier plots) to examine the trends in incident depression within and between treatment arms using the PROMIS Pediatric Depression Scale short-form..

To address the change in depressive symptoms (secondary outcome), we will examine the paired t-test in each condition, to test for any effect of either program. Subsequently, an exploratory analysis will examine the trajectory of changes over time by program arm, using graphical representations of outcomes at each time point by subject, cohort, and program arm as well as longitudinal random effects models. Hence, a within-group model would include terms for the follow-up depression score, the overall intercept, the cohort effect, the time effect, and a cohort\*time interaction—to allow the trajectory to vary by cohort—as well as random effects for individual subjects and subjects nested within cohorts.

Additional explorations will include bivariable associations (correlation, simple regressions) between the process measures and the outcome, between intervention assignment and process measures, between intervention assignment and potential mediators, and between process measures and outcomes. If indicated, mediation analyses will be conducted to investigate possible mechanisms; strength of mediation (indirect effect) will be calculated as the product of the association of the causal variable on the mediator and the association of the mediator on the outcome variable.

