Appendix B.e: PROMIS Pediatric Short Form (version 1.1)

Weekly measure for participants during 8-week intervention

PROMIS® Pediatric Item Bank v.1.1 - Depressive Symptoms - Short Form 8b

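### No PROMIS depression score is clearly scheduled before teens learn their group, and the PROMIS baseline that sections 7.1 and 9.6.1 rely on is not defined

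*Combined protocol and SAP*

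**What the plan says.** Table 3 (section 6.1) separates an online step, headed "Before Visit 2 (online" with the bracket closed, from Visit 2 at W0. The online step carries the questionnaires, the parent measures and randomization. The row "Weekly depression", which is the PROMIS form according to section 7, has no mark there or at Visit 1. Its first mark is at W0, in the same column as the credibility form.

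Three other places tie PROMIS to the course:
- Table 2: "Weekly from the beginning of the intervention"
- The measure description in section 5.1.3: it "will be used as a safety measure once participants are in the 8-week course"
- Appendix B.e: "Weekly measure for participants during 8-week intervention"

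After the first two groups, randomization takes place a week before the first class (section 6.2.2). The online links go out at the same point, and disclosure follows their return: "Once measures are completed, study staff will notify the participants of their group assignment" (section 6.2.3, Visit 2).

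Two sections need a PROMIS starting value. Section 7.1 refers a teen at T = 70 or after a rise of 3 SD "from the baseline score on the PROMIS depression measure". Section 9.6.1 plans to examine "change in depression scores (combined SMFQ-C, PROMIS Pediatric Depression Score" (bracket closed). No section says which form supplies that value. Section 9.5.1 makes T = 70 on PROMIS the incident-depression event, with 65 as a fallback, analysed by Kaplan-Meier plots and Cox models.

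**The concern.** PROMIS entered the study as a safety form (section 5.1.2) and was later made the time-to-event measure. Its calendar is still that of a form used during the program. The SMFQ-C, the resilience scale and the mediator scales all belong to the questionnaire set returned before disclosure. The scale that defines the primary exploratory outcome is not marked in that step.

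If the W0 form serves as baseline and is completed after disclosure, any reaction to the assignment is built into the starting value. Two consequences follow. A between-arm comparison of PROMIS change loses that reaction. And a teen at T of 70 or more at W0 cannot be classed as already there or newly there, which matters for an outcome called incident.

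**Working it through.** No sample size, power or event figure in the plan depends on this point, so there is none to reproduce. The check is of order in time, followed by three consequences.

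**1. PROMIS against disclosure.** Table 3 by column:

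| Row | First mark |
|---|---|
| Questionnaires | online step before Visit 2 |
| Randomization | online step before Visit 2 |
| Weekly depression (PROMIS) | Visit 2, W0 |
| Credibility | Visit 2, W0 |

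Return of the questionnaires triggers disclosure, and PROMIS comes one column later. Taken as printed, the table gives no PROMIS form before randomization and none clearly before disclosure.

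**2. PROMIS against the first class.** Section 6.2.3 numbers the eight classes as Visits 3 to 10, with Visit 6 at week 4 and Visit 10 at week 8. Counting back, Visit 3 is week 1 and class 1, so W0 would precede any class. But the credibility form is completed at the end of the first class (sections 5.1.3 and 5.2.1) and is marked at W0. These cannot both hold. Whether W0 precedes class 1 is therefore undetermined, and the credibility mark cannot date the PROMIS form.

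**3. Change contrast.** Let θ be the true between-arm difference at follow-up, δ the between-arm difference at W0 caused by disclosure or the first class, and b the slope of follow-up on baseline.
- Raw change contrast = θ − δ, so the error is δ.
- Baseline-adjusted contrast = θ − bδ, so the error is bδ.

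The documents give neither δ nor b. Assuming δ from 1 to 5 T-points and b from 0.5 to 0.9:
- Raw error: 1 to 5 points.
- Adjusted error: 0.5 × 1 = 0.5 up to 0.9 × 5 = 4.5 points.

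This shows sensitivity and is not an estimate of bias. If δ = 0, both errors are 0.

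**4. Rise rule.** Section 9.5.1 puts 70 at 2 SD and 65 at 1.5 SD above the population mean.
- SD = (70 − 65) / (2 − 1.5) = 10
- Mean = 70 − 2 × 10 = 50
- 3 SD = 30 points
- The rise rule and the T = 70 rule coincide at a baseline of 70 − 30 = 40.

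At any baseline of 40 or more, T = 70 is reached no later than the 3-SD rise. The choice of baseline form matters to this rule only below 40, if SD means the population SD. The Data Safety Monitoring Plan (Expected Risks, and section 7.3) uses T = 70 with no 3-SD figure.

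**5. Time to event.** Section 9.5.1 gives no rule for a teen at T of 70 or more on the first form. Such a teen could count as an event at time zero or as not at risk. A pre-disclosure score would separate the two; a W0 score of uncertain timing does not. The documents give no count of such teens.

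**The case against.** The best opposing reading is that W0 PROMIS belongs with the baseline set. Section 6.2.3 describes the pre-disclosure questionnaires under the name Visit 2, and several other sections call the baseline questionnaires Visit 2. PROMIS would then come before disclosure. That reading is possible. Against it stand the separate column in Table 3 and the three statements that start PROMIS with the course. If it is what was intended, the table needs the same correction.

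The mechanism is also limited. PROMIS asks about the past 7 days, so even a form completed at class 1 mostly covers the week before it. That week can still include knowledge of the group. Section 5.2.1 withholds the program names and presents both programs as beneficial. The Data Safety Monitoring Plan mentions a distress reaction to self-compassion practice, but describes it as less common and usually weaker in teens.

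A reader might draw four stronger conclusions that the documents do not support:
- *That none of the 80 teens has a PROMIS score from before they knew their group.* This is an inference from a schedule that is inconsistent with itself, not a recorded fact.
- *That a contaminated baseline is subtracted in the primary analysis.* Time to T = 70 subtracts no baseline. The ANCOVA in section 9.5.2 is for the SMFQ, and Table 2 assigns change in depression scores to the SMFQ-C. PROMIS change rests on one parenthesis in section 9.6.1.
- *That safety monitoring is materially weakened.* Step 4 of the working shows otherwise.
- *That the bias is a known share of the expected effect.* Setting an assumed shift of 1 to 3 points against the youth effect cited in section 2.2 (0.37 × 10 = 3.7 points) gives 27% to 81%. That only restates the assumption, and the cited effect is for psychological symptoms in general.

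Finally, section 9.5.1 describes PROMIS collection in the past tense, so a change to the schedule may come too late for some or all teens. That stands, and the fix needs an analysis-side part.

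**Conclusion.** The point holds as a gap in schedule and definition. The plan uses a PROMIS baseline in two places, names no form for it, and schedules no PROMIS score that is clearly before disclosure. Treating W0 as the baseline is itself an inference, made because W0 is the earliest form marked.

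The reach is limited to the exploratory PROMIS change contrast and to separating existing from incident T of 70 or more. The change error equals the W0 shift, or slope times shift after adjustment, and the size of that shift is unknown. The SMFQ baseline is unaffected. The change is worth making because it is cheap and removes the ambiguity; it does not rest on a demonstrated bias.

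**What to change.** **For teens not yet started**
- Add the eight PROMIS items to the online baseline link and mark the weekly depression row in the online column of Table 3.
- Require the form back before disclosure, and ideally before randomization, since that column also holds randomization.
- Define this score as the PROMIS baseline in sections 7.1 and 9.6.1, and keep W0 as the first on-program form. The referral thresholds are not at issue here.
- State whether W0 falls before or after the first class.

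Cost: one table cell, two definitions and about one minute per teen.

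**For teens already enrolled without such a score**
- State that W0 is post-assignment, and do not present change from W0 as change from a pre-assignment baseline.
- Use the pre-disclosure SMFQ-C as the baseline covariate in between-arm PROMIS comparisons.
- Report the time-to-event analysis with and without teens at T of 70 or more at W0.

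Cost: no new data. The SMFQ-C is a different scale, so it may adjust less well than a PROMIS score would. Leaving out teens at T of 70 or more at W0 may also remove early reactions to assignment, which is why both versions should be shown.

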## Visits 3-10 (8 weeks of Classes)

Adolescents attend the 8 weeks of classes. Classes will be audio recorded to evaluate the fidelity of the instructor to the program.

### *Visit 6 (Week 4 of Classes)*

At week 4 of the intervention (Visit 6), adolescents complete a set of questionnaires online.

### *Visit 10 (Week 8 of Classes)*

At week 8, adolescents participate in a focus group designed to obtain feedback about the program. The focus group will be audio recorded.

In addition, adolescents complete another set of online questionnaires. Study staff will send a link to the study questionnaires to the adolescents and parent one week following completion of the 8-week class. See [schedule of evaluations](#) and list of [measures](#) above.

## Visits 11-16 (Continuation Classes—see [6.2.5](#) for final visit)

At each continuation class, adolescents will review and practice what they learned in the 8-week classes. Both the adolescents and their parents will complete questionnaires 22 weeks post-intervention (Visit 13) and 36 weeks post-intervention (Visit 16). At Visit 16, adolescents will participate in a brief post-participation interview. See [schedule of evaluations](#) and list of [measures](#) above.

## 6.2.5: Completion/Final Evaluation

At the end of the continuation phase, participants will complete the final on-line questionnaires.

## Early Discontinuation from Study Intervention

Potential reasons for early termination include:

- 1) Subject no longer interested
- 2) Adverse events
- 3) Subject not able or willing to follow the protocol
- 4) Subject moved away from the area.

If subjects withdraw early, the PI or a designee will follow-up by telephone to inquire about health status as it relates to adverse events experienced by the subject leading to early discontinuation of participation.

## 7. SAFETY ASSESSMENTS

---

Participant safety is monitored through daily diaries (monitored by study staff), weekly depression assessments (PROMIS Pediatric Depression short form), and contact with program instructors (weekly during program, monthly during continuation phase). Participants exhibiting increased symptoms of depression are evaluated by the Study Psychologist and referred for further evaluation. Further details on safety are found in the study's Data Safety Monitoring Plan (DSMP, [Appendix IV](#)).

### 7.1: Specification of Safety Parameters

Combined SMFQ-C / SMFQ-P scores of 12 is the recommended cut-off value for MDD; this value or greater will generate follow-up with the study psychologist. In addition, a T score of 70 or an increase of 3 standard deviations from the baseline score on the PROMIS depression measure will generate a referral to the study psychologist.

### 7.2: Methods and Timing for Assessing, Recording, and Analyzing Safety Parameters

- 1) Timing: every contact with the participant will be an opportunity to capture adverse events.
- 2) Recording: each incidence of an adverse event will be recorded in REDCap.
- 3) Analyzing: the PI will be informed of all adverse events and will forward the information to the IRB and the Independent Safety Monitoring Committee (ISMC) (See DSMP).

### 7.3: Adverse Events and Serious Adverse Events

Adherence to current definitions and submission guidelines for identification and reporting to the IRB of Adverse Events (AEs), including Serious AEs (SAEs), and Unanticipated Problems (UPs) is planned. Reporting of all adverse events will be the responsibility of the PI ([name]). The project manager and research assistant will assist the PI with summarizing, recording, and reporting all AEs. The PI will be informed of each AE by direct subject communication or by members of the research team. Subjects will be encouraged to report, in a timely fashion, any incidents of discomfort, or a change in health status for any reason, to the research personnel.

It will be the responsibility of the PI, with assistance from the project manager and research assistant, to respond to IRB directives growing out of adverse events, including but not limited to, development and implementation of corrective action plans. The reporting process has recently been streamlined and made available online to investigators. It is also the responsibility of the PI to implement corrective action for SAEs, at times, in advance of IRB review of the incident.

#### 7.3.1: Definitions

An adverse event (AE) is any untoward medical occurrence in a subject during participation in a clinical study or with use of the experimental agent being studied. An adverse finding can include a sign, symptom, abnormal assessment (laboratory test value, vital signs, electrocardiogram finding, etc.), or any combination of these regardless of relationship to participation in the study.

A serious adverse event (SAE) is any AE that results in one or more of the following outcomes:

- Death
- A life-threatening event
- Inpatient hospitalization or prolongation of existing hospitalization
- A persistent or significant disability/incapacity
- A congenital anomaly or birth defect
- An important medical event based upon appropriate medical judgment

### 7.3.2: Classification of AE Severity

Classification of AEs will be based on the Common Terminology Criteria for Adverse Events (CTCAE) Version 4, 2009. AEs will be described by symptom or condition/diagnosis, and graded for severity (mild, moderate, or severe) — depending on the intensity of the event. Two additional categories will be used based on the CTCAE system, “life threatening” and “death”.

Grade 1. Mild: asymptomatic or mild symptoms; clinical or diagnostic observations only; minimal impact on subject’s life; intervention not indicated.

Grade 2. Moderate: medical care sought; significant but limited inconvenience on Activities of Daily Living (ADL) or lifestyle; local or noninvasive intervention indicated.

Grade 3. Severe: medically significant but not immediately life-threatening; disabling; limiting self-care; substantial disruption to the subject’s well-being; hospitalization or prolongation of hospitalization indicated.

Grade 4. SAE. Life-threatening consequences; urgent medical intervention indicated.

Grade 5. SAE. Death: related to AE.

An AE that is graded as severe (Grade 3) can be distinct from an SAE (Grades 4 and 5). A subject could experience a severe AE (Grade 3) that does not meet the definition of an SAE (see above). Alternatively, a subject could experience a moderate AE (fever, mild confusion) that meets the SAE definition (example - need for antibiotics to combat a life threatening infection).

### 7.3.3: AE Attribution Scale

AEs will also be classified on an assessment of relatedness to the study intervention. AEs will be categorized according to the likelihood that they are related to the study intervention. They will be labeled as: 1) definitely related, 2) definitely unrelated, 3) probably related, or 4) possibly related to the study intervention in the opinion of the PI and Study Psychologist after review of the circumstances and relevant records.

## 7.4: Reporting Procedures

No events will be solicited. Unsolicited events will be captured by query at each subject contact after enrollment and through the diaries.

A dated log of AEs, UPs, and SAEs will be kept in the study database. Data captured will include a detailed description of each incident, experience, or outcome. In addition, staff will include an explanation of why the AE, incident, experience, or outcome is considered a UP. The PI will determine and the project manager will document any changes to the protocol or corrective action taken or

proposed in response to a UP.

To satisfy the requirement for prompt reporting, unanticipated problems will be reported using the following timeline:

- Unanticipated problems that are serious adverse events will be reported to NCCIH within 7 days of the investigator becoming aware of the event.
- The PI, within 24 hours, will report all related or possibly-related AND serious adverse events (SAE) occurring in subjects to the IRB. This will be accomplished by submitting an adverse event report to the IRB and to the ISMC. Serious adverse events will be reported even if the PIs and Study Psychologist believe that the adverse events are unrelated to the protocol.
- Unexpected (but not serious) adverse events occurring in subjects which, in the opinion of the Study Psychologist, are possibly related to participation AND place subjects or others at a greater risk of harm than was previously known or recognized in the protocol will be reported by the PI within 24 hours of discovery by email or phone to the IRB and the ISMC. A follow-up written report within 5 business days to the IRB and the ISMC will be submitted by the PI.
- Unanticipated problems involving risks to subjects or others (UPIRTSOs) will be reported to the IRB and DSMB via email or telephone within 24 hours of discovery and a written follow up report within 5 business days.
- Any other unanticipated problem will be reported to the IRB, Independent Safety Monitor(s), and NCCIH within 14 days of the investigator becoming aware of the problem.
- When a protocol deviation occurs, the investigator will report the occurrence to the IRB. The investigator will make the determination whether the deviation meets the criteria for an unanticipated problem involving risks to subjects or others. The IRB Chair or IRB staff member will also make the determination if the protocol deviation meets the definition of an unanticipated problem involving risks to participants or others.

All unanticipated problems will be reported to appropriate institutional officials (as required by an institution's written reporting procedures), the supporting agency head (or designee), and OHRP within one month of the IRB's receipt of the report of the problem from the investigator.

SAEs that are unanticipated, serious, and possibly related to the study intervention will be reported to the Independent Safety Monitor(s), IRB, and NCCIH in accordance with requirements.

- Unexpected fatal or life-threatening AEs related to the intervention will be reported to the NCCIH Program Office, and ISMC within 3 days of the investigator becoming aware of the event. Other serious and unexpected AEs related to the intervention will be reported within 7 days.
- Anticipated or unrelated SAEs will be handled in a less urgent manner but will be reported to the Independent Safety Monitor(s), IRB, and other oversight organizations in accordance with their requirements and will be reported to NCCIH on an annual basis.

- All other AEs documented during the course of the trial will be reported to NCCIH on an annual basis by way of inclusion in the annual report and in the annual AE summary which will be provided to NCCIH and to the Independent Monitors. The Independent Safety Monitor(s) Report will state that all AEs have been reviewed.
- All AEs documented during the course of the trial will be reviewed by the Independent Safety Monitoring Committee (ISMC) on a regular basis. The ISMC will meet initially after the first cohort (20) subjects have completed the intervention and are in the continuation phase of the study. The ISMC will meet every 36 weeks thereafter.

